8.1 Dose Levels

Dose Level	MGCD516 Dose
-3	Off protocol therapy
-2	80 mg orally daily
-1	100 mg orally daily
0	120 mg orally daily*

^{*} Note: The starting dose of Sitravatinib was modified from 150 to 120 mg daily in 5/2018. Patients already enrolled on the study at the time of this modification may continue at the 150 mg dose level, or reduce to the 120 mg dose level, at the discretion of the treating investigator. For patients continuing at 150 mg, 120 mg represents dose level -1, and so on.

8.2 Management Advice for Non-Hematologic Adverse Events

Hypertension	Management/Next Dose for MGCD516
≤ Grade 1	No change in dose

Hypertension	Management/Next Dose for MGCD516		
Grade 2	Continue therapy. Institute anti-hypertensive agent or alter dose of		
Grade 2	existing anti-hypertensive agent.		
	Hold therapy. Institute anti-hypertensive agent or alter dose of		
	existing agent. Resume therapy when hypertension resolved to grade		
Grade 3	2 or less. For subsequent occurrences at grade 3, hold therapy until		
	blood pressure resolves to grade 2 or lower, and reinstitute at one		
	dose level lower, at investigator's discretion.		
Grade 4	Off protocol therapy.		

When anti-hypertensive therapy is indicated, the agent employed should be based upon review of the patient's clinical history to determine the most appropriate agent, with cardiology consultation as needed. The use of dihydropyridine calcium channel blockers such as nifedipine, amlodipine and nicardipine can be considered as first line agents, in the absence of contraindications.

Palmar Plantar Erythrodysesthesia	Management/Next Dose for MGCD516	
≤ Grade 1	No change in dose. Counsel on measures to mitigate the effects of palmar plantar erythrodysesthesia and institute topical therapies as described below.	
Grade 2	Hold until ≤ Grade 1, counsel on measures to mitigate the effects of palmar plantar erythrodysesthesia, and resume at one dose level lower.	
Grade 3	Hold until ≤ Grade 1, counsel on measures to mitigate the effects of palmar plantar erythrodysesthesia, and resume at one dose level lower, at investigator's discretion.	
Grade 4	Not applicable.	

Signs and symptoms of palmar plantar erythrodysesthesia include redness, swelling, pain and blistering on the palms of the hands and soles of the feet. Patients should be counseled to avoid exposure of hands and feet to hot water and other sources of heat, to avoid activities causing force or friction, and to avoid contact with harsh chemicals. Treatment includes the use of moisturizing agents, topical anesthetics, topical anti-inflammatory medications, and topical corticosteroids.

Proteinuria	Management/Next Dose for MGCD516
≤ Grade 1	Continue therapy with close monitoring by urinalysis at least every cycle.
Grade 2	Hold protocol therapy. Perform 24 hour urine collection to confirm degree of proteinuria. May reinstitute at one dose level lower if and when protein levels decrease to 2g in 24 hours, at the discretion of the principal investigator.
Grade 3	Off protocol therapy.
Grade 4	Not applicable.

Patients who develop more than 2g proteinuria should undergo 24 hour urine collection for definitive assessment of urine protein. Patients who develop nephrotic syndrome should be

Proteinuria	Management/Next Dose for MGCD516	
taken off protocol therapy and referred for further management by a nephrologist. ACE		
inhibitor therapy is permitted in study patients as clinically indicated.		

Diarrhea	Management/Next Dose for MGCD516
< Grade 1	No change in dose. Evaluate for infectious etiology if clinically
≥ Grade 1	indicated. Institute anti-diarrheal therapy.
	No change in dose. Evaluate for infectious etiology if clinically
	indicated. Institute anti-diarrheal therapy. If diarrhea persists at grade 2
Grade 2	or higher for more than 5 days despite supportive care, hold protocol
Grade 2	therapy and manage supportively. Reinstitute at same dose when
	symptoms improve to \leq grade 1. On subsequent occurrences at grade 2,
	consider dose reduction when therapy reinstated.
	Hold until ≤ Grade 1. Evaluate for infectious etiology if clinically
Grade 3	indicated. Institute anti-diarrheal therapy. Reinstitute at one dose level
	lower when symptoms improve to \leq grade 1.
Grade 4	Off protocol therapy.

If clinically indicated, evaluate patients for an infectious etiology of diarrhea using appropriate test for Clostridium difficile, stool cultures, and PCR for GI pathogens, where available. Treat infection as clinically indicated. First line supportive care should be instituted with the anti-diarrheal loperamide.

Fatigue	Management/Next Dose for MGCD516	
≤ Grade 1	No change in dose.	
Grade 2	No change in dose.	
Grade 3	Hold until \leq Grade 2. Resume at same dose level. If recurs at grade 3, hold until \leq Grade 2 and then resume at one dose level lower.	
Grade 4	Not applicable.	

Fatigue is commonly associated with receptor tyrosine kinase inhibitors. Evaluate and treat for other conditions which can manifest as fatigue, including but not limited to thyroid dysfunction, infection and anemia.

Left ventricular systolic dysfunction	Management/Next Dose for MGCD516
≤ Grade 1	Not applicable.
Grade 2	Not applicable.
Grade 3	Off protocol therapy.
Grade 4	Off protocol therapy.

Liver Function Abnormality	Management/Next Dose for MGCD516
	Continue study drug. Monitor liver function testing weekly until tests
ALT or AST $\geq 3x$	return to normal or baseline, or demonstrate stabilization (if tests
ULN but $\leq 5x$ ULN	demonstrate stability in the opinion of the investigator, monitoring may
$\underline{\mathbf{AND}}$ TB $\leq 2x$ ULN	be changed to every 2-3 weeks.) If liver function testing worsens,
	follow applicable instructions below.
	Hold study drug. Monitor liver function testing weekly until tests
ALT or AST $\geq 5x$	return to normal or baseline. Reinstitute therapy at one dose level lower
ULN $\underline{\mathbf{AND}}$ TB $\leq 2x$	and monitor liver function testing at least weekly for a minimum of 4
ULN	weeks after restarting therapy. If ALT or AST again $\geq 5x$ ULN,
	discontinue further protocol therapy.
	Hold study drug. Monitor liver function testing weekly until tests
	return to normal or baseline. Reinstitute therapy at one dose level lower
$TB \ge 2x ULN but \le$	and monitor liver function testing at least weekly for a minimum of 4
3x ULN regardless	weeks after restarting therapy. Note: If patient enters the study with TB
of AST/ALT	between ULN and 1.5x ULN (because attributed to presence of
	metastatic disease), no intervention is required unless increase in TB
	represents a change from baseline.
$TB \ge 3x ULN$	Discontinue study drug.
regardless of	
AST/ALT	

Protocol modifications of 6/8/2017 reflect the lack of clinically significant hepatotoxicity observed in the phase 1/1b study of Sitravatinib in solid tumors (grade 3/4 AST/ALT observed in less than 3% of patients, no grade 3/4 TB abnormalities observed. (TB = total bilirubin).

All Other Non- Hematologic Events	Management/Next Dose for MGCD516		
	Treatment delay	Dose Modification	
≤ Grade 1	No delay	No change in dose	
Grade 2	In general, hold until ≤ grade 1 or return to baseline	Not required	
Grade 3 or 4 manageable with supportive care.	Hold until ≤ grade 1 or return to baseline	Not required	
Grade 3 or 4 not manageable with supportive care.	Hold until ≤ grade 1 or return to baseline	Resume at one dose level lower than dose inducing toxicity.	

Modifications apply to toxicities deemed related to study drug. Appropriate supportive care should be instituted.

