Single dose pharmacokinetic parameters were evaluated in 24 patients, and steady state parameters in 20 patients. Plasma samples for pharmacokinetic analyses were collected over a 168-hour period following single dose administration and a 24-hour period following repeat dose administration. Drug concentrations were determined using a validated LC MS/MS method. After single administration, the drug reached peak concentration over a median time of 3 to 9 hours. Plasma exposure levels were found to increase in a dose proportional fashion. Mean elimination half-life varied between 40 and 53 hours. Steady state pharmacokinetics were reached in 11-15 days. Drug accumulation was observed following multiple dosing, averaging 4.2-fold for C_{max} and 4.7-fold for AUC₀₋₂₄. Mean value for peak to trough fluctuation was 53.8%. At the 100 mg dose level, mean steady state C_{avg} was 123 ng/mL, C_{max} was 151 ng/mL and AUC was 2590 ng*h/mL.

On 2/6/2018, Mirati Therapeutics provided updated guidance to investigators participating on the industry sponsored phase 1/1b study of Sitravatinib in solid tumors. In this study, Sitravatinib appeared to have improved long-term tolerability at a dose of 120 mg based on assessment of toxicities observed in patients starting at this dose, and in patients dose reduced from 150 to 120 mg. Furthermore, analysis of pharmacokinetic data suggest plasma concentrations for Sitravatinib are comparable at the 120 and 150 mg dose levels. Therefore, the recommended starting dose of Sitravatinib for the phase 1/1b study was modified to 120 mg, which has also been adopted in this study effective in 5/2018. Patients already enrolled on this study may continue at the 150 mg dose level, or reduce the 120 mg level, as determined by the treating investigator.

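### The liver table in section 8.2 has no stop for recurrent ALT/AST ≥5x ULN when bilirubin is between 2x and 3x ULN, but has one when bilirubin is lower

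*Combined protocol and SAP*

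**What the plan says.** The liver function table in section 8.2 has four rows.

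- **Row 1:** ALT or AST 3x to 5x ULN with TB ≤2x ULN. Continue the drug and monitor.
- **Row 2:** ALT or AST ≥5x ULN with TB ≤2x ULN. Hold until tests are normal or back to baseline, restart one dose level lower, and test at least weekly for at least 4 weeks. A recurrence rule follows: "weeks after restarting therapy. If ALT or AST again" is at or above 5x ULN, "discontinue further protocol therapy".
- **Row 3:** TB from 2x up to "3x ULN regardless" of AST/ALT. The hold, restart and monitoring are the same as in row 2. After that comes only a note on patients whose bilirubin was already raised at entry.
- **Row 4:** TB ≥3x ULN, whatever the AST/ALT. "Discontinue study drug".

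Below the table, the 2017 modifications are explained by phase 1/1b experience: "grade 3/4 AST/ALT observed in less than 3% of patients, no grade 3/4 TB abnormalities observed".

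Section 8.1 gives the dose ladder as 120, 100 and 80 mg, with level -3 being "Off protocol therapy". Section 3.2 adds that "Patients already enrolled on this study may continue at the 150 mg dose level", and the note in 8.1 says "For patients continuing at 150 mg, 120 mg represents dose level -1, and so on". Section 8 removes a patient who needs a delay of more than 28 days or more than three reductions, and describes the algorithms as recommended.

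**The concern.** The rule for a second event should become stricter, or at least no looser, as the liver picture worsens. With ALT/AST ≥5x ULN throughout, the table instead gives a stop on recurrence when TB is ≤2x, no stop on recurrence when TB is between 2x and 3x, and an immediate stop when TB is ≥3x. The middle step is the most lenient on recurrence, although both tests are raised there.

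The gap depends on which row the first event falls in. Row 2's recurrence sentence carries no bilirubin condition, so a patient who starts in row 2 stops at the next ALT/AST ≥5x even if TB is then 2x to 3x. A patient who starts in row 3 has no such rule. What is at stake is one further re-exposure to the drug after a combined ALT/AST and bilirubin rise. No efficacy result is affected.

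**Working it through.** No figure in the plan needs reproducing. The check is of table logic, followed by a count of restarts and a ceiling on frequency.

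**1. Which row applies.** The four triggers were applied as printed to ALT/AST of 5x, 6x and 10x ULN.

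| TB (x ULN) | Matching row | Rule on recurrence of ALT/AST ≥5x |
|---|---|---|
| 1 | 2 (also row 1 at exactly 5x) | Stop |
| 2.01, 2.5, 2.99 | 3 only | None |
| 3.5 | 4 | Already stopped |

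Bilirubin rows overlap only at exactly 2x (rows 2 and 3) and exactly 3x (rows 3 and 4). Making the upper bounds strict leaves row 3 as the only match between 2x and 3x, so a misread inequality sign does not explain the gap. Because only one row applies there, the section 8 rule for conflicting recommendations (take the lowest dose) has nothing to resolve.

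**2. Restarts from 120 mg.** Assume ALT/AST ≥5x at every event and recovery within 28 days each time. Row 2's recurrence sentence applies at any TB, row 3 always steps down one level, and row 4 stops.

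| First event | All later events | Restarts |
|---|---|---|
| Row 2 | Row 2 | 1 |
| Row 2 | Row 3 | 1 |
| Row 3 | Row 3 | 2 (100, then 80 mg) |
| Row 3 | Row 2 | 1 or 2 |
| Row 2 or 3 | Row 4 | 1 |
| Row 4 | – | 0 |

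In the row 3 then row 2 order, the count is 1 if the word for a repeat event in row 2 covers any earlier ALT/AST ≥5x event, and 2 if it covers only earlier row 2 events. Repeated row 3 events give 2 − 1 = 1 restart more than repeated row 2 events. The stop comes at the third event, and it comes from the dose ladder, not the liver table.

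**3. Patients who stayed at 150 mg** (enrolled before the change in 5/2018). Repeated row 3 events give 2 restarts (120, 100 mg) if level -3 still means off treatment. They give 3 (120, 100, 80 mg) if 80 mg is kept, which is exactly the three-reduction cap. Row 2 gives 1 on either reading.

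**4. Frequency.** Take the phase 1/1b rate of grade 3/4 AST/ALT, below 3%, as a proxy for ALT/AST ≥5x ULN (an assumption).

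- 0.03 × 29 = 0.87 patients
- 0.03 × 31 = 0.93 patients, with the two extra patients allowed by section 15.2

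This ceiling counts every ALT/AST ≥5x event. The documents do not say what share has TB above 2x or recurs. Purely as illustration, suppose 10% to 50% of such patients have TB between 2x and 3x, and 25% to 50% of those recur in the same pattern:

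- low: 0.87 × 0.10 × 0.25 = 0.02 patients
- high: 0.87 × 0.50 × 0.50 = 0.22 patients

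**The case against.** The strongest reply is that this matters very little. The tables are headed as advice and described as recommended, and sections 7.3 and 8 let the investigator end treatment for an unacceptable or intolerable event. Tests must return to normal or baseline before any restart, long delays remove the patient, the ladder runs out, and the DSMC follows every treated patient for toxicity. Several other tables, such as grade 3 diarrhea and grade 4 neutropenia, also order a reduced restart with no recurrence stop, so row 2 is the exception. The 2017 note shows that some leniency on liver events was chosen deliberately. The row 3 then row 2 order may not be a gap at all, since row 2's wording naturally covers any earlier ALT/AST ≥5x event. The 150 mg counts depend on a separate ambiguity in the dose table and concern an unstated number of patients.

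Most of this stands as a limit on size. It does not remove the point. Discretion permits a stop but does not require one, and the general limits act later than the first recurrence. Row 2 shows that the authors did not leave recurrent ALT/AST ≥5x to judgment. Low overall hepatotoxicity is no reason for a looser rule when bilirubin is also raised. Row 3 also covers isolated bilirubin rises, which may explain why it has no bilirubin recurrence rule, but nothing in the protocol explains the absence of the ALT/AST one.

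**Conclusion.** The concern holds and is minor. As written, a first event with ALT/AST ≥5x ULN and TB between 2x and 3x ULN carries no stop on recurrence, while the same ALT/AST with lower bilirubin does. From 120 mg the excess is one restart, at 80 mg, in the order row 3 then row 3, and possibly in the order row 3 then row 2. This assumes the table is followed literally and tests recover within 28 days each time. The number of patients affected lies between zero and the ceiling of 0.87 of 29 (0.93 of 31), most likely near the lower end. The Simon decision rule and the 12-week progression-free rate are unaffected. This is a patient-safety consistency correction.

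**What to change.** Add one sentence to row 3: if ALT or AST was at or above 5x ULN at the earlier event and reaches that level once more after restart, whatever the bilirubin, protocol treatment ends permanently. This brings row 3 into line with row 2, settles the row 3 then row 2 order, and leaves isolated bilirubin rises handled as they are now. It can go into the next amendment and needs no extra tests, visits or patients.

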5.1 Inclusion Criteria

5.1.1	Stage 1: Histologically confirmed well-differentiated or dedifferentiated
	liposarcoma. If stage 1 of the Simon II stage design fails to meet its endpoint for
	liposarcoma patients, an additional 16 patients will be enrolled, composed of 4 each
	of MPNST, synovial sarcoma, alveolar rhabdomyosarcoma and alveolar soft part
	sarcoma (otherwise, an additional 16 patients with well-differentiated or de-
	differentiated liposarcoma would be enrolled). Pathology review occurs at the
	center enrolling the patient on this trial.
5.1.2	Disease must be locally advanced and unresectable or metastatic. Disease which
	may be resected but with an associated level of morbidity deemed unacceptable by
	the treating clinician is considered eligible.
5.1.3	Patients must have measurable disease by RECIST criteria version 1.1.
5.1.4	Patients must evidence of disease progression, either clinically or radiographically,
	within the 12 weeks prior to study enrollment, as determined by the investigator
	enrolling the patient on the study.
5.1.5	Patients must have been treated with at least one prior systemic regimen for
	sarcoma. Neoadjuvant or adjuvant systemic therapy qualify as prior therapy for the
	purposes of this study. There is no upper limit on previous lines of therapy
	received. A prior line of systemic therapy may include prior investigational agents
	received as part of other clinical studies.
5.1.6	Patients must be age 18 years or older. Because no dosing or adverse event data are
	currently available for MGCD516 in patients less than 18 years of age, children are
	excluded from the present study, but will be eligible for future pediatric trials.
	. 2

5.1.7	Patients must demonstrate an ECOG perfo	ormance status of 0 or 1.
5.1.8	Patients must demonstrate normal organ and marrow function as defined below:	
	Absolute neutrophil count (ANC) Platelet count Creatinine Calculated creatinine clearance Total bilirubin AST/ALT	≥ 1,500/mm ³ ≥ 100,000/mm ³ ≤ 1.5 times upper limit of normal OR > 45 mL/min* ≤ 1.5 times upper limit of normal** ≤ 1.5 times upper limit of normal**
	Notes: Upper limit of normal is defined by the cli	inical laboratory performing the test.

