	* Using the lean body mass formula only * If transaminase elevation and/or bilirub of liver metastases, a total bilirubin ≤ 2.5 t AST and ALT ≤ 2.5 times the upper limit an elevated bilirubin level that is attributed Gilbert's disease, may be enrolled at the d	oin elevation is attributed to the presence times the upper limit of normal and an of normal are permissible. Patients with d to an inherited disorder, such as
5.1.9	Patients must demonstrate adequately controlled blood pressure at the time of study entry, as defined by a blood pressure ≤ 150/100 mmHg at study screening on at least one of two screenings conducted at least 24 hours apart. If blood pressure meets these guidelines on initial measurement, no subsequent measurement for screening is needed. Blood pressure may be assessed by automated or manual methods by an appropriately trained clinician or nurse.	
5.1.10	Patients must have normal left ventricular transthoracic echocardiogram or MUGA sejection fraction.	systolic function, as demonstrated by a
5.1.11	The effects of MGCD516 on the developing reason, women of child-bearing potential a contraception (hormonal or barrier method study entry and for the duration of study pregnant or suspect she is pregnant while study, she should inform her treating physenrolled on this protocol must also agree to study, for the duration of study participation MGCD516 administration. If patients do reconsidered eligible.	and all men must agree to use adequate d of birth control, abstinence) prior to participation. Should a woman become she or her partner is participating in this sician immediately. Men treated or o use adequate contraception prior to the on, and 4 months after completion of
5.1.12	Ability to understand and willingness to s	ign a written informed consent document.

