timeframe may be used for screening purposes. Imaging studies are performed every 2 cycles (6 weeks, 42 days) for the first 36 weeks of study treatment, and then every 3 cycles (9 weeks, 63 days) thereafter. Imaging studies may be performed +/- 5 days from the required date. In the event of dose delays/holds, imaging studies should still be obtained at the scheduled timepoints as determined from registration, without delays to account for the dose delays/holds. Confirmatory scans must be obtained at least 4 weeks after the documentation of an objective response as discussed in section 12. It is acceptable to perform confirmatory assessments at the next appointed evaluation per protocol. Response assessment should include assessment of all sites of disease and use the same imaging method as used at baseline whenever possible.

- (3) All laboratory studies may be performed +/- 3 days from the required date.
- (4) Comprehensive metabolic panel is to include albumin, alkaline phosphatase, total bilirubin, bicarbonate, blood urea nitrogen, calcium, chloride, creatinine, glucose, potassium, total protein, AST, ALT and sodium.
- (5) Applies to liposarcoma patients only: All patients will have their most recent available biopsy material submitted for next generation sequencing to assess for genetic alterations of MGCD516 targets. See section 13 for more information on sample collection, processing and analysis. In cases were institutional policy or availability of prior specimens preclude this analysis, these studies will not be performed for that patient.
- (6) Applies to liposarcoma patients only: A subset of 10 patients will undergo baseline and ontreatment tumor biopsies for RPPA studies. The first 10 patients with lesions amenable to biopsy who are enrolled to the study (beginning with the first patient enrolled in stage I) will undergo these biopsies. See section 13 for information on sample collection, processing and analysis. The baseline biopsy specimen will be obtained at any point between day -14 and the date of first treatment with the study drug (cycle 1, day 1) provided consent is obtained and the other eligibility criteria are met. The on-treatment biopsy specimen will be performed with a target timepoint of cycle 1 day 15 (with a window of cycle 1 days 15 through 20). Biopsies will be obtained from the site of disease. If the study fails in stage I and proceeds to the exploratory cohort, no further RPPA analyses will be performed.

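### The bilirubin exemption in 8.2 stops at 1.5x ULN, so it never operates in its own 2x–3x row and misses liver-metastasis patients admitted at 2.0–2.5x ULN

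*Combined protocol and SAP*

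**What the plan says.** **Entry.** Inclusion criterion 5.1.8 sets the general limit for total bilirubin at "≤ 1.5 times upper limit of normal". No reason for the elevation is required up to that level. A footnote raises the limit when the elevation is put down to the presence "of liver metastases, a total bilirubin ≤ 2.5 t"; the line is cut in extraction, but the 2.5x ULN limit is readable. The same footnote mentions inherited bilirubin disorders in a broken line: "of normal are permissible. Patients with d to an inherited disorder, such as". The readable text breaks off before any condition or cap on that group can be seen.

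**On treatment.** The liver function table in 8.2 has a row for total bilirubin from 2x to 3x ULN, whatever the transaminases. Drug is held until tests "return to normal or baseline. Reinstitute therapy at one dose level lower", and the site must then "and monitor liver function testing at least weekly for a minimum of 4" weeks. At 3x ULN or more, drug is discontinued.

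**The note.** Inside the 2x–3x row, a note waives intervention for patients whose entry bilirubin was "between ULN and 1.5x ULN (because attributed to presence of" metastatic disease, unless the value has risen from baseline.

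**The concern.** The note is meant to stop an entry elevation caused by metastases from being handled as drug toxicity. It pairs the metastasis rationale with the general entry limit of 1.5x ULN, where attribution plays no part, and not with the 2.5x ULN limit, where attribution is what makes the patient eligible. The patients who need the exemption are therefore outside it, and those inside it cannot use it.

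At stake is a dose reduction, or a series of them, triggered by the value at which the protocol admitted the patient. This concerns dosing and safety rules only. It does not bear on the progression-free rate at 12 weeks, the two-stage decision rule or its error rates.

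**Working it through.** The plan states no figure on this point, so there is none to reproduce. The check compares thresholds, all in multiples of ULN.

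| Item | Range | Source |
|---|---|---|
| General entry limit | up to 1.5 | 5.1.8 |
| Entry limit, liver metastases | up to 2.5 | 5.1.8 footnote |
| Hold-and-reduce row | 2.0 to 3.0 | 8.2 liver table |
| Baseline note | 1.0 to 1.5 | 8.2, same row |
| Discontinuation row | 3.0 or more | 8.2 liver table |

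1. **Can the note operate in its row?** A covered patient has a baseline of at most 1.5. To reach 2.0 the value must rise by at least 2.0 − 1.5 = 0.5x ULN, or 2.0/1.5 − 1 = 33.3%. That is a rise from baseline, so the note's own exception removes the waiver. Stepping baseline and on-treatment values from 0.5 to 4.0 in steps of 0.05, and counting pairs that lie in the row and are exempted because the value has not risen, gives 0 pairs with the limit at 1.5.
2. **Could it operate elsewhere in the table?** No. The first two rows are triggered by AST or ALT, and bilirubin alone below 2.0 triggers no row.
3. **Who is in the row without exemption?** The overlap of the liver-metastasis entry range with the row is 2.0 to 2.5. Patients entering from above 1.5 to below 2.0 are outside the note too, but an unchanged value there triggers no hold.
4. **What does the literal rule do to them?** A stable value already satisfies the baseline restart condition, so the patient restarts one level down. From section 8.1 this is 120 to 100 mg: (120 − 100)/120 = 16.7%. For a patient still on 150 mg it is 150 to 120 mg: 30/150 = 20%. If bilirubin stays where it was, the row could be met again after restart: from a 120 mg start, 100 to 80 mg, then off protocol therapy.
5. **What would a limit of 2.5 do?** On the same grid it exempts 66 pairs. These are the 11 baselines from 2.00 to 2.50, each with on-treatment values from 2.00 up to baseline: 11 × 12 / 2 = 66.
6. **Is there still a safety stop?** Yes. From an entry value of 2.5, a rise of 3.0/2.5 − 1 = 20% reaches the discontinuation row.

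**The case against.** The strongest reply is that section 8 is not meant for unchanged baseline values. Its preface offers guidance for adverse events attributed to the drug and judged intolerable. The 8.2 heading speaks of advice on adverse events. Section 9.2 counts a preexisting condition as an adverse event only if it worsens. A sentence in 8.2 limits modifications to drug-related toxicity. A pre-dose bilirubin that has not moved cannot be attributed to the drug. The literal reading also defeats itself, because it would admit a patient and then step that patient off treatment for the value accepted at entry.

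Much of this stands, and it makes the literal reading less likely. It does not dispose of the point. The relatedness sentence is printed under the separate table for all other non-hematologic events. The authors also wrote a specific baseline exemption into this row, and one that stops at 1.5x ULN invites the inference that higher baselines are not exempt. None of the general texts corrects that limit.

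Three stronger readings should be resisted:

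- A reader might infer that patients with Gilbert's disease or similar are caught in the same way, or even by the 3x ULN stop. The footnote is cut off just where it begins to say how they may be enrolled, so a cap or condition may be lost. The documents do not settle it.
- A reader might infer that sites will handle such patients differently. Nothing in the documents shows this.
- A reader might take the first row's phrase, "demonstrate stability in the opinion of the investigator, monitoring may" be relaxed, as a precedent for letting investigator opinion decide the bilirubin hold. There it governs only how often to test while drug continues.

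**Conclusion.** The mismatch is established on the text. Eligibility reaches 2.5x ULN for liver metastases, the hold row starts at 2x, and the note ends at 1.5x, so the note exempts nobody and stable entrants at 2.0x to 2.5x ULN are left uncovered. A dose cut follows only if a site applies the row literally, which the framing of section 8 makes less likely.

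The severity is minor. The documents give no frequency for liver-metastasis patients in this range. The number is probably small among 29 planned patients, and may be zero. Nor do the documents show that 100 mg is less active than 120 mg, so no loss of efficacy should be inferred. The conclusion assumes that the readable limits in 5.1.8 and 8.2 are as intended; the documents do not say which of the two the authors would change.

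**What to change.** In the 8.2 note, replace the entry range with: above ULN and up to 2.5x ULN, because attributed to liver metastases, as permitted by 5.1.8. Keep the existing condition that intervention is needed only if bilirubin has risen from baseline. Add one sentence: patients entering at 2x ULN or above have liver tests weekly for the first 4 weeks. Leave the 3x ULN discontinuation row unchanged.

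The added sentence matters because the exemption would otherwise remove the weekly testing that the row requires after restart. With 21-day cycles, the study calendar schedules panels on days 1, 8, 15, 22 and 43. Weekly testing for four weeks means days 8, 15, 22 and 29, so the cost is one extra panel per such patient, on day 29. Calendar note 4 confirms the content: "Comprehensive metabolic panel is to include albumin, alkaline phosphatase, total bilirubin", with AST and ALT also listed.

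The retained condition gives no size for a rise, so a move from 2.2x to 2.3x ULN could still count. The plan already leaves that open.

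The alternative is to lower the liver-metastasis entry limit to below 2x ULN. That is more cautious, but it narrows eligibility and leaves the note without effect.

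Separately, the sponsor should check the full text of the inherited-disorder criterion and decide whether that group needs the same exemption.
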